1. PROTOCOL SYNOPSIS

Title of Study:	A Clinical Study to Assess the Skin Barrier Impact of Winlevi
Study Period:	2 weeks
Test Products:	Winlevi Apply twice daily to entire randomized side of face (product applied to randomized forehead, cheek, and jawline).
Objective:	The objective of this study is to demonstrate the lack of barrier damage induced by Winlevi as measured by corneometry and TEWL.
Design:	Female or male subjects with acne prone skin will be enrolled in this split face single site study evaluating the barrier effects of Winlevi. Subjects who sign consent and meet all inclusion criteria and none of the exclusion criteria will be enrolled at the baseline visit. Subjects will be asked to continue their own, self-selected cleanser and sunscreen throughout the 2-week study with equal application to both sides of the face. The sunscreen and cleanser must have been used for 30 days prior to study enrollment without difficulty. Subjects must apply Winlevi twice daily to the randomized right or left face. Subjects will receive a compliance diary and the blinded study treatment product to be applied to the randomized half face following cleansing, every morning and evening. The assessing dermatologist investigator will be blinded as to which side of the face is receiving the Winlevi treatment. Subjects will be seen at baseline, 24 hours, week 1, and week 2. The dermatologist investigator and subjects will assess tolerability for each side of the face separately at each visit on a 5 point ordinal scale. Noninvasive TEWL and corneometry assessments of both sides of the face will be conducted at baseline, 24 hours, week 1, and week 2. Subjects will complete their study participation at week 2. The compliance diary and all study products will be collected at this time. Women of child bearing potential will be administered a urine pregnancy test at baseline and week 2.
Study	Healthy female or male subjects 18+ years of age of all Fitzpatrick skin types
Population:	who self identify as having sensitive acne prone skin.
Number of Subjects:	50 subjects
Inclusion	1. Subjects who self identify as having sensitive acne prone skin.
Criteria:	 Female or male subjects 18+ years of age. Subjects with Fitzpatrick skin types I-VI.

	 Subject agrees not to introduce any new colored cosmetics (lipsticks, eye shadows, facial foundations, blush, powder) or skin care products during the study. Subjects must be willing to use only a cleanser and sunscreen on the
	entire face and no other skin care products.
	6. Subjects must be willing to use the Winlevi study product to designated half face. No other topical acne treatment products on the entire face for the 2 week duration of the study.
	 Subject has signed an Informed Consent Form in compliance with 21CFR Part 50: "Protection of Human Subjects."
	 Subject is dependable and able to follow directions and is willing to comply with the schedule of visits.
	9. Subject is in generally good physical and mental health.
Exclusion	1. Any dermatological disorder, which in the investigator's opinion, may
Criteria:	interfere with the accurate evaluation of the subject's skin
	characteristics, except for the conditions associated with sensitive skin.
	2. Subjects who are not willing to use only the assigned study product and
	nothing else one randomized half face, except for cleanser and
	sunscreen that must remain unchanged during the study. Moisturizers
	or topical acne treatment products should not be used during the 2
	week study period on either side of the face.
	 Subjects who do not agree to refrain from direct sun exposure during the study duration.
	 Subjects who have demonstrated a previous hypersensitivity reaction to any of the ingredients of the study products.
	5. Subjects, who are pregnant, breast feeding, or planning a pregnancy.
	6. Subjects with clinically significant unstable medical disorders.
	Subjects who are unwilling or unable to comply with the requirements of the protocol.
	 Subjects who have history of a psychological illness or condition that would interfere with their ability to understand and follow the requirements of the study.
	9. Subjects who are currently participating in any other clinical study.
	10. Subjects with any planned surgeries and/or invasive medical
	procedures during the course of the study.
	11. Subjects who currently or frequently use high doses of anti-
	inflammatory drugs for a defined medication condition. Aspirin use should not exceed 2 tablets (650 mg) per day.
	12. Subjects currently receiving any anticancer, immunosuppressive
	treatments/ medications (e.g., azathioprine, belimumab,
	cyclophosphamide, Enbrel, Imuran, Humira, mycophenolate mofetil,
	methotrexate, prednisone, Remicade, Stelara.), or radiation as
	determined by the initial paperwork.
	13. Subjects with a history of immunosuppression/immune deficiency
	disorders (including (HIV infection or AIDS) or currently using
	immunosuppressive medications (e.g., azathioprine, belimumab,

	cyclophosphamide, Enbrel, Imuran, Humira, mycophenolate mofetil, methotrexate, prednisone, Remicade, Stelara) and/or radiation as determined by study documentation.
Endpoints:	Primary Endpoint: The primary endpoint is the change in corneometry reading between the two sides of the face treated with Winlevi versus no treatment.
	Secondary Endpoints: The secondary endpoint is the change in TEWL reading between the two sides of the face treated with Winlevi versus no treatment.
Measures:	Dermatologist Investigator assessed tolerability parameters: dryness, erythema, scaling, and irritation will be assessed separately for each side of the face. All assessments will be made on a 5-point ordinal scale (0=none, 1=minimal, 2=mild, 3=moderate, 4=severe) at baseline, 24 hours, week 1, and week 2.
	Subject assessed tolerability parameters: dryness, tightness, stinging, itching, and burning will be assessed separately for each side of the face. All assessments will be made on a 5-point ordinal scale (0=none, 1=minimal, 2=mild, 3=moderate, 4=severe) at baseline, 24 hours, week 1, and week 2.
	Noninvasive Biomeasurements : TEWL and corneometry measurements on the right and left cheek will be conducted at baseline, 24 hours, week 1, and week 2.
Statistical Methods:	Along with descriptive statistics (means, standard deviations and percentages), investigator ordinal nonparametric data will be analyzed using Wilcoxon signed rank test and sign test for paired comparison at different time points. The noninvasive parametric data will be analyzed using paired t-test. Change will be considered significant at the alpha level of 0.05.

2. STUDY VISIT SCHEDULE

	Visit 1	Visit 2	Visit 3	Visit 4
Procedures	BL	24 Hours	Week 1	Week 2
Informed Consent Procedure	X			
Inclusion/Exclusion Criteria	X			
Brief Medical History and Concomitant Medications Review	X	X	X	X
Investigator Clinical Grading for Tolerability	x	X	X	x
Subject Clinical Grading for Tolerability	x	X	X	Х
Product Dispensing	X			
TEWL (both facial sides)	x	X	X	X
Corneometry (both facial sides)	x	X	X	X
Urine Pregnancy Test (WOCP)	x			Х
Adverse Events		X	X	X
Subject Diary Assessment and Compliance Check	S R	x	X	х
Subject Product Accountability and Study Completion				х

3. INTRODUCTION

Acne medications are a common source of facial dryness resulting in skin barrier damage and poor patient compliance. Retinoids and benzoyl peroxide are some of the most frequently prescribed and effective acne medications, however, dryness is an unwanted side effect. A new acne medication, 1% clascoterone, has been placed in a novel vehicle for excellent drug delivery in combination with excellent barrier properties. The barrier properties of 1% clascoterone have never been demonstrated. This study is aimed at better understanding the positive barrier effects of 1% clascoterone.

4. STUDY OBJECTIVE

The objective of this study is to demonstrate the lack of barrier damage induced by Winlevi as measured by corneometry and TEWL.

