8.3 NONCOMPLIANT SUBJECTS

Subjects who are found to be noncompliant will be queried as to the reason for their noncompliance. If noncompliance results from study product problems, full interviews will be conducted by the investigator to determine the nature and severity of the problem and an adverse event will be recorded. Subjects who are noncompliant will be released from their study participation and their last visit data carried forward.

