9.1 COMPLETED, DISCONTINUED OR INCOMPLETE SUBJECTS

A completed subject is a subject who has satisfied all study entry criteria and completed the 2-week study. For any subject who has started study and terminates the study prematurely, efforts will be made to obtain final evaluations of clinical status. Reasonable efforts will be made to contact any subject lost to follow-up during the course of the study in order to complete assessments and retrieve any outstanding data and clinical supplies. The investigator will choose the description that best describes the status of the subject at termination.

1. Subject completed the 2-week study period

OR INCOMPLETE/DISCONTINUED DUE TO:

- 2. Contact dermatitis
- 3. Adverse experience
- 4. Serious adverse experience
- 5. Pregnancy
- 6. Protocol violation
- 7. Subject withdrew consent
- 8. Subject lost to follow-up
- 9. Other

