10.6 CODE DISCLOSURE

A randomization code will be maintained indicating which side of the face received the currently marketed Winlevi. An independent blinded dispenser who is not associated with other study activities will randomize the study products and maintain the randomization until data lock occurs.

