12. STATISTICAL METHODS

Along with descriptive statistics (means, standard deviations and percentages), investigator and subject ordinal nonparametric results will be analyzed using Wilcoxon signed rank test and sign test for paired comparison at different time points. The noninvasive parametric results will be analyzed using paired t-test. Changes will be considered significant at the alpha level of 0.05.

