12.1 SAMPLE SIZE RATIONALE

A sample size of 50 study subjects was chosen by the study sponsor.

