12.2 SIGNIFICANCE LEVEL

Significance is defined at the p < 0.05 level based on a two-sided test.

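### The objective is to demonstrate lack of barrier damage, but the plan gives corneometry and TEWL only a two-sided test of no difference, with no margin, confidence-interval rule or decision visit

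*Combined protocol and SAP*

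**What the plan says.** The synopsis and section 4 state the same single objective: "The objective of this study is to demonstrate the lack of barrier damage induced by Winlevi as measured by corneometry and TEWL". Sections 12.5.1 and 12.5.2 make the change in corneometry the primary endpoint and the change in TEWL the secondary endpoint, each comparing the Winlevi side with the untreated side. Neither names a visit, although section 8.1 schedules readings at baseline, 24 hours, week 1 and week 2.

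For inference, section 12 says: "The noninvasive parametric results will be analyzed using paired t-test". Section 12.2 adds: "Significance is defined at the p < 0.05 level based on a two-sided test". Planned descriptive statistics are means, standard deviations and percentages. The Wilcoxon and sign tests are for the ordinal tolerability scores, not for these two measures. On sample size, section 12.1 says only: "A sample size of 50 study subjects was chosen by the study sponsor".

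Section 8.3 bears on any conclusion of no damage: "Subjects who are noncompliant will be released from their study participation and their last visit data carried forward".

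**The concern.** A two-sided paired t-test takes no difference as its null hypothesis. Rejecting that null shows a difference; failing to reject it does not show that there is none, and a smaller or noisier sample makes failure more likely. The objective asks for the absence of harm, and the plan has no criterion for concluding it. Only a significant difference in favour of Winlevi would argue against damage, and that is more than the objective requires.

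If the product is simply neutral, the plan therefore defines no result that meets its only objective. How a non-significant p-value is read, and at which of three visits, stays open until the results are known.

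**Working it through.** **Inputs from the documents.** 50 subjects, each giving one pair of sides (sections 6.2 and 12.1); paired t-test (section 12); two-sided 0.05 (section 12.2); three post-baseline readings (section 8.1).

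**Assumptions.** The documents give no SD, no size of change that counts as damage, no power and no dropout rate. The figure of 50 therefore cannot be reproduced. Effects below are in SDs of the paired side difference in change, taken as normal, at one visit, with complete data unless stated. I take damage to mean lower corneometry or higher TEWL; the plan does not state the direction.

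**1. Chance of a non-significant result when there is worsening.** The critical value is t(0.975, 49) = 2.010, and the noncentrality is d × √50.

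| True worsening d | d × √50 | P(p >= 0.05), 50 pairs | P(p >= 0.05), 40 pairs |
|---|---|---|---|
| 0.2 SD | 1.414 | 0.716 | 0.765 |
| 0.3 SD | 2.121 | 0.452 | 0.543 |
| 0.4 SD | 2.828 | 0.208 | 0.306 |

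Losing pairs makes a non-significant result more likely. These would be error rates only if p >= 0.05 were read as no damage and if a change of that size were damage.

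**2. Chance of a significant benefit when the effect is exactly zero.**
- One prespecified visit: 0.05 / 2 = 0.025 per measure, whatever the sample size.
- A benefit at any of three visits: 1 − 0.975³ = 0.073 if visits are independent, and about 0.049 by simulation with correlation 0.8 between visits. The range is about 5% to 7%.

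**3. What a confidence-interval rule could deliver.** The 95% interval has half-width 2.010 / √50 = 0.284 SD. If the true difference is zero, the power to exclude a margin m is P(T > 2.010), where T is noncentral t with 49 degrees of freedom and noncentrality m × √50.

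| Margin m | Power, 50 pairs | Pairs for 80% power |
|---|---|---|
| 0.2 SD | 28% | 199 |
| 0.3 SD | 55% | 90 |
| 0.4 SD | 79% | 52 |
| 0.5 SD | 93% | 34 |

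If the true worsening equals the margin, the rule wrongly concludes no damage 2.5% of the time per measure with complete data.

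**4. Effect of carry-forward on that rule.** Suppose 10 of 50 subjects are carried forward (assumed), the true final worsening and the margin are both 0.3 SD, and the carried values average c times the final worsening. The apparent mean worsening is 0.3 × (40 + 10c) / 50. The false no-damage rate is simulated, with carried values given the same SD as the rest.

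| c | Apparent mean worsening | False no-damage rate |
|---|---|---|
| 0 | 0.24 SD | about 6% |
| 0.5 (worsening still building) | 0.27 SD | 4.0% |
| 1 (flat) | 0.30 SD | 2.5% |
| 2 (early and transient) | 0.36 SD | 0.8% |

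The direction of the bias depends on the time course, which the documents do not give.

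**The case against.** The strongest reply is that the Introduction describes an interest in positive barrier effects. The two-sided test may therefore be meant to find a benefit, and a significant benefit would indeed argue against damage on that measure. That is fair as far as it goes. But it is background text, it is not repeated as an objective, and it leaves a neutral result without a rule.

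A second reply is that an interval can be computed from the planned means and SDs. It can, if the SD is that of the paired differences, but without a margin fixed beforehand it is not a decision rule.

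A third is that this is a two-week, single-site study of a marketed product, so the stakes are modest. That affects how elaborate the remedy must be. It does not affect whether the analysis can answer the objective.

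Three stronger readings are tempting, and the documents do not support them:
- **That the plan will treat p >= 0.05 as proof of no damage.** It nowhere says so. The gap is that it states no criterion.
- **That carry-forward must favour a conclusion of no damage.** It does so if worsening builds over time and does the opposite if worsening is early and transient. Visit 2, at 24 hours, includes both a compliance check and instrument readings, so many carried subjects could have a reading taken after treatment began. Carrying everyone at zero change is an extreme case.
- **That 50 subjects are too few.** Without an SD or a margin, that cannot be judged.

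**Conclusion.** The point stands. The only objective is a claim of no damage, and the planned test cannot establish it for a product that is merely harmless. This follows from the text and needs no assumed SD.

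The probabilities in the working show size only. They rest on normality, one visit, 50 complete pairs and effects in assumed SD units. The 2.5% chance of a significant benefit under no effect needs no SD, but it holds for one prespecified visit; because the plan names none, 5% to 7% is possible if any visit may count. Carry-forward is a further uncertainty of unknown direction, not the core of the problem.

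**What to change.** Before data lock, and so before the code described in section 10.6 is released, amend section 12 to:

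- name one decision visit, for example week 2;
- report the Winlevi-minus-untreated difference in change, with a two-sided 95% confidence interval, for both measures;
- conclude lack of damage on corneometry only if the lower limit is above −M1, and on TEWL only if the upper limit is below +M2, with M1 and M2 justified in instrument units;
- state the power of 50 subjects for those margins;
- report how many subjects are carried forward under section 8.3, and show the result with and without carry-forward.

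If no margin can be justified, remove the claim to demonstrate absence of damage from the objective, report the 95% intervals, and state that p >= 0.05 is not evidence of no damage.

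**Cost.** A protocol revision, which section 14.4 makes subject to written approval from the sponsor and the IRB, plus the work of justifying two margins. No added visits or measurements are needed. The main downside is that the result may be inconclusive with 50 subjects if the margin is narrow: power is 28% at 0.2 SD and 55% at 0.3 SD. Analysing without carry-forward also loses pairs: at a 0.4 SD margin, power falls from 79% to 75% with 45 pairs and 69% with 40.

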5. STUDY DESIGN OVERVIEW

Female or male subjects with acne prone skin will be enrolled in this split face single site study evaluating the barrier effects of Winlevi. Subjects who sign consent and meet all inclusion criteria and none of the exclusion criteria will be enrolled at the baseline visit. Subjects will be asked to continue their own, self-selected cleanser and sunscreen throughout the 2-week study with equal application to both sides of the face. The sunscreen and cleanser must have been used for 30 days prior to study enrollment without difficulty. Subjects must apply Winlevi twice daily to the randomized right or left face.

Subjects will receive a compliance diary and the blinded study treatment product to be applied to the randomized half face following cleansing, every morning and evening. The assessing dermatologist investigator will be blinded as to which side of the face is receiving the Winlevi treatment. Subjects will be seen at baseline, 24 hours, week 1, and week 2. The dermatologist investigator and subjects will assess tolerability for each side of the face separately at each visit on a 5 point ordinal scale. Noninvasive TEWL and corneometry assessments of both sides of the face will be conducted at baseline, 24 hours, week 1, and week 2.

Subjects will complete their study participation at week 2. The compliance diary and all study products will be collected at this time. Women of child bearing potential will be administered a urine pregnancy test at baseline and week 2.

6. STUDY POPULATION

6.1 POPULATION DESCRIPTION

Healthy female or male subjects 18+ years of age of all Fitzpatrick skin types who self identify as having sensitive acne prone skin.

6.2 POPULATION SIZE

50 subjects

6.3 INCLUSION CRITERIA

The following items represent the inclusion criteria:

- 1. Subjects who self identify as having sensitive acne prone skin.
- 2. Female or male subjects 18+ years of age.
- 3. Subjects with Fitzpatrick skin types I-VI.
- 4. Subject agrees not to introduce any new colored cosmetics (lipsticks, eye shadows, facial foundations, blush, powder) or skin care products during the study.
- 5. Subjects must be willing to use only a cleanser and sunscreen on the entire face and no other skin care products.
- 6. Subjects must be willing to use the Winlevi study product to designated half face. No other topical acne treatment products on the entire face for the 2 week duration of the study.
- 7. Subject has signed an Informed Consent Form in compliance with 21CFR Part 50: "Protection of Human Subjects."
- 8. Subject is dependable and able to follow directions and is willing to comply with the schedule of visits.
- 9. Subject is in generally good physical and mental health.

6.4 EXCLUSION CRITERIA

The following items represent the exclusion criteria:

- 1. Any dermatological disorder, which in the investigator's opinion, may interfere with the accurate evaluation of the subject's skin characteristics, except for the conditions associated with sensitive skin.
- 2. Subjects who are not willing to use only the assigned study product and nothing else one randomized half face, except for cleanser and sunscreen that must remain unchanged during the study. Moisturizers or topical acne treatment products should not be used during the 2 week study period on either side of the face.
- 3. Subjects who do not agree to refrain from direct sun exposure during the study duration.
- 4. Subjects who have demonstrated a previous hypersensitivity reaction to any of the ingredients of the study products.
- 5. Subjects, who are pregnant, breast feeding, or planning a pregnancy.
- 6. Subjects with clinically significant unstable medical disorders.
- 7. Subjects who are unwilling or unable to comply with the requirements of the protocol.
- 8. Subjects who have history of a psychological illness or condition that would interfere with their ability to understand and follow the requirements of the study.
- 9. Subjects who are currently participating in any other clinical study.
- 10. Subjects with any planned surgeries and/or invasive medical procedures during the course of the study.

- 11. Subjects who currently or frequently use high doses of anti-inflammatory drugs for a defined medication condition. Aspirin use should not exceed 2 tablets (650 mg) per day.
- 12. Subjects currently receiving any anticancer, immunosuppressive treatments/ medications (e.g., azathioprine, belimumab, cyclophosphamide, Enbrel, Imuran, Humira, mycophenolate mofetil, methotrexate, prednisone, Remicade, Stelara.), or radiation as determined by the initial paperwork.
- 13. Subjects with a history of immunosuppression/immune deficiency disorders (including (HIV infection or AIDS) or currently using immunosuppressive medications (e.g., azathioprine, belimumab, cyclophosphamide, Enbrel, Imuran, Humira, mycophenolate mofetil, methotrexate, prednisone, Remicade, Stelara) and/or radiation as determined by study documentation.

6.5 CONCOMITANT MEDICATIONS

No topical medications are allowed on the face. No facial skin care products other than sunscreen and cleanser are allowed on the face. The subject must have used the self-selected sunscreen and cleanser for at least 30 days without difficulty.

